CECIDOC Study

Combination of ECG and Cardiovascular risk factors could Increase Diagnostic performance Of Chest pain triage at ED

Study Protocol and Statistical Analysis Plan 04-09-2019

[name], [name], [name], [name], [name], [name], [name], [name].

Université Catholique de Louvain

St Luc University Hospital

PI : [name]

[contact]

Background

Acute chest pain triage in the Emergency Department (ED) may prove challenging, since similar symptoms can reveal both mild or life-threatening disorders, and the clinical presentation itself is known not to be reliable for evaluating the risk of acute coronary syndrome (ACS)^{1,2}.

The first priority in patients with suspected ACS is to identify those with ST-elevation myocardial infarction (STEMI), since these patients require urgent reperfusion therapy. Both European and American cardiology guidelines recommend implementation of a 12-lead electrocardiogram (ECG) within 10 min of arrival in the ED^{3,4}.

In contrast, in the absence of electrocardiographic changes consistent with ischemia, the ACS rate is low (1–8% depending on the number of risk factors)³, and ACS are associated with lower in-hospital mortality ^{4,5,6}.

Emergency Department (ED) triage systems for acute chest pain are either based on clinical features or on a 12-lead ECG. A recent study showed the systems having a similar diagnostic performance but different characteristics since clinical-based triage had a higher sensitivity and ECG-based triage had a higher specificity⁷. The lack of sensitivity of ECG based triage was explained by the fact that patients with a normal or non-ischemic ECG were assigned to a low-acuity triage score, defined as inadequate (false negative) for ACS patients. Conversely, the lack of specificity of clinical based triage was due to a large number of patients with benign pathology assigned to a high-acuity triage score to perform a 12-lead ECG within the 10 minutes after the first medical contact as required.

We therefore hypothesized that combination of 12-lead ECG and cardiovascular risk factor could increase the sensitivity of ECG based triage for chest pain patients with a normal or non-ischemic ECG.

Methods

Selection of participants

All consecutive patients above 18 years of age, presenting at ED with acute non-traumatic chest pain as main complaint will be systematically included in the study.

Study design

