We plan a prospective, single-center, observational study in a teaching hospital in Brussels, Belgium.

Triage of chest pain patients will be performed using the "French Emergency Nurses Classification version 2" (FRENCH) triage system⁸, which is currently used in our ED. FRENCH score is a 5-levels triage system classifying patients from category 1 corresponding to the "immediately life-threatening condition" to category 5 corresponding to the "less or non-urgent situations". Maximum authorized waiting period before first medical assessment according to severity category are respectively: immediate response, 20 minutes, 60 minutes, 120 minutes and undefined. Initial triage of chest pain

patients is based on vital signs, than if normal patients with a normal or unmodified ECG are sorted into category 3, those with an abnormal ECG without evidence of ischemia are classified into category 2, while those with ECG showing signs of ischemia (ST elevation, ST depression, new onset of a left bundle branch block, or T-wave inversions) are classified into category 1. Patients with lateral chest pain of a probable musculoskeletal nature are sorted into category 4 without performing an ECG.

The FRENCH triage (ECG-based triage) will be compared to a modified FRENCH triage system (ECG Score- based triage) upgrading high-risk patients with a normal ECG from category 3 to category 2. We defined high-risk patients as patients having a Systemic Coronary Risk Estimation (SCORE) above 10 % according with the 2016 European Guidelines on cardiovascular disease prevention in clinical practice⁹. To facilitate calculation of the SCORE at triage, we defined one major or four minor criteria required to upgrade the patients.

The major criteria are:

- 1. History of Cardio-vascular disease
 - a. acute coronary syndrome
 - b. stroke or IAT.
 - c. aterial revascularization procedure of peripheral artery.
- 2. Diabetes
- 3. End-stage renal disease or dialysis

The minor criteria are:

- 1. Man
- 2. Above 60 years of age
- 3. Hypertension
- 4. Smoker
- 5. Dyslipidemia

The above criteria will be collected by the triage nurse using a computerized form designed for the study. On this basis, the computer will additionally sort the patients using our modified triage scale, with blinded result avoiding bias in the initial nurse triage. This modified triage will therefore not be taken into account and management of the patients will not be modified.

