Medical data will also be collected by physicians using a dedicated computerized form, particularly cardiovascular risks factors and complications occurring during the ED stay (arrhythmia, heart failure, shock).

The final diagnosis will be determined at the end of a 30-day follow-up, by either reviewing patient's files or a phone call to patients or relatives. ECG interpretation and diagnosis of acute myocardial infarction will be based on the universal definition of myocardial infarction¹⁰. Pulmonary embolism and aortic dissection will be substantiated by computed tomography (CT), chest infection by relevant positive biomarkers and a chest X-ray, gastroesophageal reflux by gastroscopy or positive therapeutic test with a proton pump inhibitor, and abdominal pathology by biology, imaging, or both.

Musculoskeletal pain will be diagnosed if all of the above-mentioned investigations are normal, and movement and palpation enhanced superficial pain. Finally, patients with a normal physical

examination, ECG, chest X-ray, and blood tests who did not report any event during the 30-day follow-up, and who therefore have no definite cause for their chest pain, will be sorted into a dedicated group called 'unclear diagnosis'.

The local hospital ethics committee approved the study protocol (CEHF 2017/18AOU/407), and patients will provide their written informed consent to participate in this study.

Statistical methods

To evaluate triage system's diagnostic performance, we will compare the triage score of patients with ACS (final diagnosis of STEMI, non-ST-elevation myocardial infarction [NSTEMI] or unstable angina [UA]) to a control group made up of patients with chest pain from mild severity diseases (including digestive diseases, chronic obstructive pulmonary disease (COPD) exacerbation, musculoskeletal chest pain, and all unclear diagnoses without any medical event in the follow-up period). Patients with other severe diseases, abnormal heart rate, abnormal blood pressure, respiratory distress, or hypoxemia will be excluded from the control group having a triage score driven by these conditions rather than by the ECG.

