Since for ACS most of the arrhythmic events occur within 12 h of symptom onset^{11,12} and ACS patients should be monitored¹³, we defined for ACS a triage Score of 1 or 2 (high-acuity triage score) as adequate (true positive), and a triage Score of 3, 4, or 5 (low-acuity triage score) as inadequate (false negative). Conversely, for the control group with mild severity diseases, we defined a triage Score of 1 or 2 (high-acuity triage score) as inadequate (false positive), and a triage Score of 3, 4 or 5 (low-acuity triage score) as adequate (true negative). Receiver operating characteristic (ROC) curves will be generated to assess each triage system's accuracy in classifying a patient in ACS versus control group.

Capability of triage nurses to collect cardiovascular risk factors will be assessed comparing data collected at triage to these collected by the physician in the medical computerized file.

Sample Size

Based on our previous study (7), FRENCH score AUC under the ROC curve was 0.69. We hypothesized a correlation of 0.9 between the two tests. To show a difference of 0.06 between the AUC of the tests with a power of 0.8 (alpha 0.05) we calculated a sampled size of 233 patients. Given the uncertainty of the correlation, we planned to enrol 500 patients.

References

1

and non–Q wave myocardial infarction: results of the TIMI III Registry ECG Ancillary Study. J Am Coll Cardiol 30:133–140

insights from PARAGON-A applied to GUSTO-IIb1. J Am Coll Cardiol 38:64-71

- ⁶ Barrabe's JA, Figueras J, Moure C et al (2000) Prognostic significance of ST segment depression in lateral leads I, aVL, V5 and V6 on the admission electrocardiogram in patients with a first acute myocardial infarction without ST segment elevation. JACC 35(7):1813–1819
- ⁷ [name], Diego Castanares-Zapatero, Patrick Vanden Berghe, Philippe Meert, Alessandro Manara1 (2016) Comparison of clinical-based and ECG-based triage of acute chest pain in the Emergency Department. Intern Emerg Med DOI 10.1007/s11739-016-1558-8
- ⁸ Taboulet P, Moreira V, Haas L et al (2009) Triage with the French emergency nurses classification in hospital scale: reliability

and validity. Eur J Emerg Med 16(2):61-67

- ⁹ Massimo F. Piepoli (Italy), ArnoW. Hoes and all. 2016 European Guidelines on cardiovascular disease prevention in clinical practice. *European Heart Journal*, Volume 37, Issue 29, 1 August 2016, Pages 2315–2381

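### Patients with abnormal vital signs are removed from the controls but kept among the ACS patients, so each scale's sensitivity and specificity come from differently selected groups

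*Combined protocol and SAP*

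**What the plan says.** The combined protocol and SAP enrols, under Selection of participants, "All consecutive patients above 18 years of age, presenting at ED with acute non-traumatic chest pain as main complaint".

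Under Study design, the initial triage of such "patients is based on vital signs, than if normal patients with a normal or unmodified ECG are sorted into category 3". The ECG rule is thus a second step, reached only when vital signs are normal. The modified scale differs from FRENCH only by "upgrading high-risk patients with a normal ECG from category 3 to category 2".

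Under Statistical methods, the cases are "patients with ACS (final diagnosis of STEMI, non-ST-elevation myocardial infarction [NSTEMI] or unstable angina [UA", with no condition on vital signs. The controls have mild disease, and for them there is a further rule: "Patients with other severe diseases, abnormal heart rate, abnormal blood pressure, respiratory distress, or hypoxemia will be excluded from the control group". The reason comes in the same sentence: they "will be excluded from the control group having a triage score driven by these conditions rather than by the ECG".

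For ACS, the plan counts "a triage Score of 1 or 2 (high-acuity triage score) as adequate (true positive", whatever led to that category. For controls, categories 3 to 5 are true negatives. Each scale's ROC curve is built from these two groups.

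The Sample Size section states that "FRENCH score AUC under the ROC curve was 0.69" and sizes the study to detect a difference of 0.06. It does not say in which population these figures hold. No analysis with the same vital-sign rule in both groups is planned, and no section states which FRENCH category abnormal vital signs lead to.

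**The concern.** The reason for the exclusion is that the ECG did not set the triage level. By the plan's own account of triage, that is just as true of an ACS patient with abnormal vital signs, yet only controls are removed.

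Two target populations would be coherent: all ACS patients and mild-disease controls, or the subset whose level was set by the ECG. The plan takes sensitivity from the first and specificity from the second, so an AUC that combines them belongs to neither.

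If abnormal vital signs lead to category 1 or 2, the retained ACS patients are true positives on both scales, and the modification cannot move them because it acts only on category 3. Compared with exclusion from both groups, they raise FRENCH sensitivity and AUC and dilute the difference that the study is sized to detect. Compared with no exclusion, sensitivity is unchanged and specificity reads higher.

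**Working it through.** **The three rules side by side**

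| Rule | ACS patients | Mild-disease controls |
|---|---|---|
| Plan | all | normal vital signs only |
| Exclusion from both | normal vital signs only | normal vital signs only |
| No exclusion | all | all |

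The mismatch in the first row follows from the text and needs no figure. Everything below also assumes that abnormal vital signs lead to category 1 or 2, which the plan's reason for the exclusion implies but does not state.

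**Inputs**

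- From Sample Size: FRENCH AUC 0.69 and difference 0.06, taken here to hold with exclusion from both groups (an assumption).
- Assumed, among patients with normal vital signs: FRENCH sensitivity s = 0.60 and specificity 0.78, so that (0.60 + 0.78)/2 = 0.69; share of ACS upgraded u = 0.25 and of controls w = 0.13, so that (0.25 − 0.13)/2 = 0.06.
- Assumed: shares with abnormal vital signs v (ACS) and c (controls), at 5%, 10% and 20%.

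The plan's own sample size of 233 is not at issue. With two-sided alpha 0.05, power 0.8 and correlation 0.9, it is reached at about 4.3 to 4.8 controls per ACS patient (Hanley-McNeil null variance at 4.4: 43 ACS, 233 in total). The plan does not state that ratio.

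**Single cut, AUC = (sensitivity + specificity)/2, v = c = 0.10**

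- FRENCH sensitivity: s + v(1 − s) = 0.60 + 0.10 × 0.40 = 0.64 under the plan and with no exclusion; 0.60 with exclusion from both.
- FRENCH specificity: 0.78 under the plan and with exclusion from both; 0.78 × 0.90 = 0.702 with no exclusion.
- FRENCH AUC: plan (0.64 + 0.78)/2 = 0.710; both 0.690; none (0.64 + 0.702)/2 = 0.671.
- Difference, plan: ((1 − v)u − w)/2 = (0.225 − 0.13)/2 = 0.0475.
- Difference, both: (u − w)/2 = 0.060.
- Difference, none: ((1 − v)u − (1 − c)w)/2 = (0.225 − 0.117)/2 = 0.054.

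| v = c | FRENCH AUC: plan / both / none | Difference: plan / both / none |
|---|---|---|
| 5% | 0.700 / 0.690 / 0.681 | 0.054 / 0.060 / 0.057 |
| 10% | 0.710 / 0.690 / 0.671 | 0.048 / 0.060 / 0.054 |
| 20% | 0.730 / 0.690 / 0.652 | 0.035 / 0.060 / 0.048 |

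With a single cut, the plan's FRENCH AUC exceeds that with exclusion from both by v(1 − s)/2, and the modified AUC does so by v(1 − s − u)/2. The plan's FRENCH AUC exceeds that with no exclusion by c × specificity/2, and the same formula with the modified specificity applies to the modified scale. None of these is negative. The difference between scales falls by v × u/2 against exclusion from both, and by c × w/2 against no exclusion.

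**The other anchor.** Suppose instead that 0.06 was meant under the plan's own rule (w = 0.13, v = c = 0.10). Then u = (0.12 + 0.13)/0.90 = 0.278. The plan gives 0.060 by construction, exclusion from both gives (0.278 − 0.13)/2 = 0.074, and no exclusion gives 0.060 + 0.0065 = 0.0665. The order is the same.

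**ROC over the category levels.** Assume levels 1/2/3 hold 35/25/40% of ACS and 6/22/72% of controls with normal vital signs (FRENCH AUC 0.691). With p1 and q1 the level-1 shares of ACS and controls, D = [u(1 − q1) − w(1 − p1)]/2. With w = 0.10, D = 0.06 needs u = (0.12 + 0.065)/0.94 = 0.1968. At v = c = 0.10:

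- Abnormal vital signs at level 1: plan (1 − v)D = 0.054; none (1 − v)(1 − c)D = 0.0486. FRENCH AUC is 0.719 under the plan and 0.668 with no exclusion.
- At level 2: plan (1 − v)D − vw/2 = 0.054 − 0.005 = 0.049; none (1 − c) × 0.049 + (1 − v)cu/2 = 0.0441 + 0.0089 = 0.053. FRENCH AUC is 0.705 and 0.682.

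Against exclusion from both, the difference shrinks in every case. Against no exclusion, its direction depends on the category assigned and the type of ROC.

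**The case against.** The strongest defence is that the asymmetry fits a target of adequate triage. For ACS, a high-acuity category is right whatever led to it. A mild-disease patient with hypoxemia, plausible because COPD exacerbation is a control diagnosis, would be unfairly scored as over-triaged. That is a coherent wish, but it is not the reason the plan gives. It also selects on final diagnosis, so it defines no group that can be recognised at triage.

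Several other objections stand in part:

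- Sensitivity in all ACS patients is the scale's real sensitivity as used, and the illustration agrees (64% under the plan and with no exclusion). The fault is in pairing it with a specificity from a restricted group.
- Both scales are scored on the same patients. Against exclusion from both groups the effect on the difference is conservative, and no false superiority is alleged.
- The shares with abnormal vital signs and the category they lead to are not in the documents. The statements of direction depend on the category; the mismatch of populations does not.
- The fall from 0.060 to 0.048 depends on where 0.06 is anchored. Under the other anchor the plan loses nothing against its stated target, though the three rules still disagree.
- Patients with other severe diseases remain in neither group, so no version here restores the full consecutive population.

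**Conclusion.** The point holds and should be fixed. The plan applies its vital-sign exclusion to one group only, for a reason that covers both, so each AUC combines a sensitivity and a specificity from differently selected patients. That conclusion rests on the text alone.

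The size cannot be known from the documents. If abnormal vital signs lead to category 1 or 2, and 5% to 20% of each group have them, the single-cut illustration puts the plan's FRENCH AUC 0.010 to 0.040 above exclusion from both groups. The difference between scales is then 0.054 to 0.035 instead of 0.060. Against no exclusion, the direction for the difference is not fixed. Nothing is claimed about what the ECG alone would show in ACS patients with abnormal vital signs. Confidence is medium.

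**What to change.** In Statistical methods, apply the vital-sign criteria already listed for controls to ACS patients as well, for the ECG-triage comparison. Use the abnormal signs themselves, not a judgement of what set the level. Report alongside it the comparison with no vital-sign exclusion in either group. Which of the two is the target population is the sponsor's choice. State which FRENCH category abnormal vital signs lead to.

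The cost is two sentences and one rerun; the control exclusion already needs the same criteria and triage vital signs. The downside is that a share v of ACS patients leaves the restricted set.

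Precision need not suffer. Take 43 ACS patients and 233 − 43 = 190 controls with normal vital signs, v = c = 10%, the single-cut inputs above, and SE = ½√[u′(1 − u′)/n + w′(1 − w′)/m]. Here u′ and w′ are the shares upgraded among the n ACS patients and m controls analysed. Difference over SE is 0.0475/0.0341 = 1.39 under the plan, 0.060/0.0369 = 1.63 with exclusion from both (38.7 ACS), and 0.054/0.0337 = 1.60 with no exclusion (211 controls).
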